9.2 Setting

This is a study conducted in a real-world setting using primary and secondary data collected from the EBMT and CIBMTR patient registries. The registries provide robust coverage across their target regions, with the EBMT Registry estimated to capture data from 80% of all HSCT centers across Europe (Annex 2) and the CIBMTR estimated to capture all allo-HSCT and 85% of all autologous HSCT occurring within the US (Annex 3). The registry data sources are discussed further in Section 9.4 (Data Sources), Section 9.6 (Data Management), and Section 9.8 (Quality Control). All transplant centers participating in this study will report data directly to their respective transplant registry; SAEs, including hematologic malignancies, occurring among patients receiving exa-cel will additionally be reported directly to the MAH (Sections 11 and 12).

It is expected that patients recruited through both registries from both regions will be comparable because guidelines from organizations, such as the European Network for Rare and Congenital Anaemias, the American Society of Hematology, and the Thalassaemia International Federation, suggest that the standard of care across both Europe and the US for patients with SCD and TDT is similar.¹⁻⁴ Individuals with TDT receive regular transfusions and iron chelation with regular monitoring for iron accumulation in major organs and individuals with SCD are treated to reduce pain episodes, prevent stroke and other vaso-occlusive events, and monitor for potential organ damage. Though new medications are becoming available for these rare disease populations, hydroxyurea / hydroxycarbamide continues to be the standard of care, available globally and included on the World Health Organization List of Essential Medications.⁵ With respect to exa-cel, in the post-approval setting it will be only available to individuals with severe forms of disease who are fit for transplant, suggesting that treated patients will have similar levels of disease severity and baseline comorbidity regardless of the region of transplant.

This study will include patients from Germany, France, Italy, UK, and US. Within Europe, Italy, France, and UK are among the top providers of HSCT to patients with TDT and SCD (EBMT data on file).⁶ The US is among the top international providers of HSCT to patients with SCD (CIBMTR data on file). Within these 5 countries, study enrollment of both exa-cel-treated and comparator populations will take place from the participating transplant centers providing exa-cel commercially. Therefore, it is anticipated that patients receiving exa-cel post-authorization will be reflective of the eligible population in the target commercial regions and that the allo-HSCT comparators will similarly reflect the Exa-cel Cohorts' target age group for the region(s) and will receive comparable care. As indicated in Sections 9.1.1 and 9.1.2, all patients receiving exa-cel from participating transplant centers will be invited to enroll in the study. Patients receiving an allo-HSCT of any donor type or cell source and who are of an age that corresponds with the approved exa-cel label will also be invited to enroll and participate in the comparator group of the study.

All patients choosing to participate in the study will be enrolled by the transplant center at or before the time of transplant. The transplant centers have standardized forms and timepoints for reporting patient data to the patient registries. Baseline data and transplant specifics are collected by transplant centers and entered into the registry at or near the time of transplant ("Day 0"). Follow-up reporting of each individual patient's status occurs by the transplant center to the registry at standardized time intervals: 100 days, 6 months, 1 year, and then annually post-transplant. Study-specific data collection will be integrated into the transplant center reporting timelines. Patient data may be sourced by transplant center personnel directly from the transplant site or via the patient's routine healthcare provider (HCP). Further information on the data to be collected and the schedule of data collection can be found in Section 9.3 (Variables).

9.3 Variables

All variables will be as reported to the transplant registries via either the standard existing registry forms or custom, study-specific reporting forms developed jointly with the registry operators:

Standard existing registry forms:

- EBMT Core Forms
- EBMT Extended Forms
- CIBMTR Pre-Transplant Transplant Essential Data (TED)
- CIBMTR Pre-Transplant Comprehensive Research Forms (CRF) and Post-Transplant CRF

Study-specific reporting forms for primary data collection:

- EBMT study-specific form
- CIBMTR study-specific form

All outcome variables specified in Sections 9.3.3 through 9.3.5 will be evaluated for both the exa-cel and allogeneic HSCT cohorts, including the TDT Exa-cel, TDT Allo-HSCT, SCD Exa-cel and SCD Allo-HSCT Cohorts, with a few exceptions which are noted below (e.g., VOC events are only applicable to SCD cohorts). The study variables are summarized in Sections 9.3.1 through 9.3.5. The schedule of data collection is summarized in Section 9.3.6.

The current version of standard EBMT and CIBMTR data collection forms as well as mapping of study variables to these forms are provided in Annex 4. Study-specific forms are being developed with registry operators and will be finalized upon the protocol approval.

9.3.1 Primary Disease Diagnosis Variables

Variables described in this section are to allow classification of exposure and cohort allocation.

Primary disease diagnosis indicated for transplant will be as reported to the transplant registries and will include:

- β-thalassemia
- SCD

 β -thalassemia or SCD genotype will also be recorded.

These variables will allow disease classification and may allow additional inference on disease severity.

9.3.2 Exposure Variables

Receipt of an autologous HSCT with exa-cel or an allo-HSCT, with the transplant date designated as Day 0, will be as reported to the transplant registries.

- Exa-cel HSCT
- Allo-HSCT

Additional transplant details for collection (e.g., conditioning regimen) are listed in Section 9.3.5.

9.3.3 Safety Outcome Variables

Variables described in this section are specifically to characterize the safety of the transplant procedure; collection and reporting of these safety outcomes encompass the primary objective of the study.

Neutrophil recovery information will allow assessment of the initial function of the graft and identify instances of neutrophil engraftment failure. Platelet recovery information will allow characterization of any instances of delayed platelet recovery; the threshold used for defining platelet recovery in patients with SCD is higher compared to patients with β -thalassemia to protect individuals with SCD from thrombocytopenia-associated hematologic complications.⁷⁻¹¹ New malignancy diagnosis information will allow assessment of the risk of secondary malignancies post-transplant.¹² New or worsening hematologic disorder is an exploratory variable to assess any indication of bone marrow compartment regeneration abnormality.

The following safety outcomes will be recorded as summarized in the schedule of data collection presented in Section 9.3.6:

- Neutrophil recovery will be defined as the achievement of an absolute neutrophil count (ANC) of ≥500/mm³ (or ≥0.5 × 10⁹/L) for 3 consecutive measurements. Date of ANC recovery will be assigned as the date of the first of 3 consecutive measurements where the ANC is ≥500/mm³. Time to neutrophil recovery will be defined as number of days from the transplant date (Day 0) to the date of neutrophil recovery.
- Platelet recovery definition will differ based on the primary disease diagnosis:
 - For patients with β-thalassemia, platelet recovery will be defined as achievement of 3 consecutive measurements of platelets ≥20 × 10⁹/L after 7 days without platelet transfusion. Date of platelet recovery will be assigned as the first of the 3 consecutive measurements where platelets ≥20 × 10⁹/L. Time to platelet recovery will be defined as number of days from the transplant date (Day 0) to the date of recovery.
 - For patients with SCD, platelet recovery will be defined as achievement of 3 consecutive measurements of platelets \geq 50 × 10⁹/L after 7 days without transfusion. Date of platelet recovery will be assigned as the first of the 3 consecutive measurements where platelets \geq 50 × 10⁹/L. Time to platelet recovery will be defined as number of days from the transplant date (Day 0) to the date of recovery.
- **New malignancy**, including type and time to initial diagnosis, will be defined as any new malignancy, solid or hematologic, as reported to the transplant registry following the transplant date. Additional detail will be collected upon diagnosis, if available:

- TNM classification (for solid organ malignancies)
- Hematologic malignancy follow-up evaluation to be performed by the MAH as described in Section 12
- New or worsening (non-malignant) hematologic disorder, including time to diagnosis, may include the diagnosis of immune thrombocytopenia, autoimmune hemolytic anemia, autoimmune neutropenia, aplastic anaemia or other event, as reported to the transplant registry. Disorder status will be tracked at subsequent visits (e.g., stable, progressive, resolved), as applicable.
- **Mortality / Survival Status**, including time to event, will be based on the record in the respective registry:
 - Cause of death, as reported to the registries, will also be recorded
 - Date of last patient follow-up

9.3.4 Effectiveness Outcome Variables

Variables described in this section are to: (i) characterize disease status at baseline and (ii) allow direct and indirect assessment of the effectiveness and durability of the transplant. Characterization of the type and number of transfusions (among TDT and SCD patients) and/or severe VOC events (SCD patients only) pre- and post-transplant allows determination of whether overt disease symptomatology has been corrected with the transplant. Hb measures, including total Hb concentration as well as Hb fractionation (e.g., % HbS among patients with SCD), allows tracking of graft uptake and function at a more cellular level than the symptomatic measures. Iron concentration and iron overload management are secondary measures of graft function, as cessation of primary symptomology (transfusion dependence) should lead to measurable decreases in iron burden and a reduced need for iron overload therapies over time. Measures of organ dysfunction at baseline and over time are also secondary measures of graft function as successful correction of the underlying genetic deficiency is expected to prevent further accumulation of organ damage over time and/or prevent new disease-related organ damage events from occurring. These measures encompass the core effectiveness assessment for the transplant.

The following effectiveness outcomes will be recorded:

- **Primary disease severity measures** will be recorded pre- and post-transplant as summarized in the schedule of data collection presented in Section 9.3.6. Specifically, pre-transplant these events will be quantified for the 1 year (12 months) preceding initiation of the conditioning regimen:
 - RBC transfusion events (TDT and SCD) to be defined as the receipt of RBCs for the purpose of primary disease management (i.e., anemia). Number of RBC transfusions and number of units transfused will be recorded pre- and post-transplant (as available) as summarized in the schedule of data collection. Time from HSCT to most recent transfusion will be recorded.
 - Severe VOC events (SCD only): Number of severe VOC events will be recorded pre- and post-transplant as summarized in the schedule of data collection presented in Section 9.3.6. Time from HSCT to most recent severe VOC event will be recorded.

Severe VOC events will include any/all of the following events:

- Acute pain events, to be defined as an acute pain event that requires hospitalization or a visit to a medical facility for treatment
- Acute chest syndrome events, to be defined as clinical evidence of the presence of a new pulmonary infiltrate associated with pneumonia-like symptoms, pain, cough or fever, and requiring hospitalization or a visit to a medical facility for treatment
- Priapism events, to be defined as a priapism event lasting >2 hours and requiring hospitalization or a visit to a medical facility for treatment
- Splenic sequestration event, to be defined by an enlarged spleen, left upper quadrant pain, and an acute decrease in Hb concentration of $\geq 2 \text{ g/dL}$ and requiring hospitalization or a visit to a medical facility for treatment
- Hospitalization for any severe VOC event during the reporting period, to be recorded in the post-HSCT period only
- **Hb measures** will be recorded pre- and post-transplant as summarized in the schedule of data collection presented in Section 9.3.6:
 - Hb concentration, grams per deciliter (g/dL)
 - Hb fractionation measured to assess the relative proportion of Hb variants produced, including (at minimum): percent HbF, HbS (for SCD, only)
- **Iron concentration measures** will be recorded pre- and post-transplant as summarized in the schedule of data collection presented in Section 9.3.6:
 - o Serum ferritin concentration, micrograms per liter ($\mu g/L$)
 - Liver iron concentration (LIC), measured by magnetic resonance imaging (MRI), milligrams per gram dry weight (mg/g)
 - Cardiac iron concentration (CIC), measured by obtaining MRI T2* (msec)
- **Disease-related end-organ damage or dysfunction** diagnoses, including approximate time to initial diagnosis if available, will be recorded pre- and post-transplant as summarized in the schedule of data collection presented in Section 9.3.6:
 - o Anemia
 - o Arrythmia
 - Central nervous system event (stroke, ischemic or hemorrhagic; transient ischemic attack)
 - Diabetes
 - Growth retardation / impairment
 - Heart failure, congestive
 - Hepatomegaly
 - Hypogonadism

- o Hypothyroidism
- Liver cirrhosis
- Liver fibrosis
- Myocardial infarction
- Osteopenia or osteoporosis
- Osteonecrosis
- Pulmonary hypertension
- Retinopathy, SCD-related
- Renal failure
- Splenectomy, surgical
- Splenomegaly (among those with spleens)
- Ulcer(s) of the leg
- Venous thromboembolism (deep vein thrombosis, pulmonary embolism)
- **Iron overload management,** to be recorded pre- and post-transplant as summarized in the schedule of data collection presented in Section 9.3.6:
 - Chelation therapy agent (e.g., deferoxamine, deferiprone) use since last visit
 - Phlebotomy (for managing iron overload) use since last visit

9.3.5 Additional Key Variables

Additional key variables encompass general patient characteristics (e.g., demographics and health status), supporting transplant and laboratory measures (e.g., complete blood count [CBC]), and additional transplant-related complications (e.g., infection, bleeding, veno-occlusive liver disease) that may be of importance. The hematopoietic cell transplantation comorbidity index (HCT-CI) captures a wide range of co-existing diseases or organ impairments relevant to HSCT outcomes such as renal or hepatic impairment and prior history of malignancy. These variables may be considered as covariates for subgroup analyses and/or allow to further characterize the post-transplant outcomes.

Additional key variables will be recorded pre- and/or post-transplant as summarized in the schedule of data collection presented in Section 9.3.6 to assess patient demographics and general health status.

• Demographics

- Age at initial disease diagnosis
- Age at transplant
- o Sex
- Race, Ethnicity (US only)
- Country of transplant

- Payor type (US only)
- Health status
 - Performance score (Karnofsky for ages ≥ 16 years or Lansky for ages < 16 years)
 - Hematopoietic cell transplantation comorbidity index (HCT-CI) items¹³
 - Height
 - o Weight
 - Smoking history
- Additional transplant details will be recorded at the time of transplant, as available.
 - Preparative regimen (myeloablative, reduced-intensity, non-myeloablative, unknown)
 - Conditioning agent(s), including dose, start date, as available
 - \circ CD34⁺ cell infused dose, if available
 - Mobilization agent (Exa-cel Cohorts only)
 - Product identification (Exa-cel Cohorts only)
 - Donor type (Allo-HSCT Cohorts only)
 - Donor matching (Allo-HSCT Cohorts only)
 - Cell source (Allo-HSCT Cohorts only)
- **Disease-related therapy** use will be recorded pre- and post-transplant as summarized in the schedule of data collection presented in Section 9.3.6, to be defined as prescription or in-hospital use (i.e., for opioids) of the below agents or interventions at any time in the 1 year prior to HSCT (pre-transplant) or since the prior visit (post-transplant):
 - o Crizanlizumab
 - o Hydroxyurea / Hydroxycarbamide
 - o L-glutamine
 - Luspatercept
 - Narcotics / Opioids (for indication-related pain, only)
 - Non-narcotic and/or nonsteroidal anti-inflammatory drug analgesics (for indication-related pain, only; if available)
 - Voxelotor
 - Other [with write-in field] to allow flexibility over time, a write-in field will be available to capture additional therapies not specified at the time of study initiation
- Additional laboratory measures will be recorded pre- and post-transplant, as available, as summarized in the schedule of data collection presented in Section 9.3.6:
 - CBC
 - RBC count

- White blood cell count
- Hb (included in Section 9.3.4)
- Hematocrit
- Mean corpuscular volume
- Platelet count
- Reticulocyte count
- o Erythropoietin
- Soluble transferrin receptor
- Lactate dehydrogenase
- Liver function measures
 - Alanine transaminase / Alanine aminotransferase
 - Aspartate transferase / Aspartate aminotransferase
 - Bilirubin, Total
 - Bilirubin, Direct
 - Bilirubin, Indirect
- Glomerular filtration rate, estimated (eGFR)
- **Transplant-related complications,** including time to initial diagnosis, to be recorded post-transplant as summarized in the schedule of data collection presented in Section 9.3.6:
 - Infection (including site, organism)
 - Bleeding events (including site)
 - o Veno-occlusive disease / sinusoidal obstruction syndrome
 - o Non-infectious interstitial pneumonitis / idiopathic pneumonia syndrome
 - Graft-versus-host disease (acute, chronic)
- **Pregnancy report**, including delivery date, for patient or partner (outcomes: live birth, stillbirth, spontaneous abortion, elective or therapeutic abortion, not yet delivered, other).
 - For live births, if available, to also collect instances of small for gestational age, intrauterine growth retardation, other.

9.3.6 Schedule of Data Collection

Data collection for each patient will occur on the following schedule: Baseline / Day 0 report, Day 100, 6-month and 1-year assessments, then annual assessments thereafter.

Data will be collected using registry standard and study-specific forms. Mapping of variables to standard collection or study-specific collection is included in Annex 4.

In addition to the data collection in the registry databases, all SAEs including hematologic malignancy, regardless of causality, among exa-cel recipients starting at the time of exa-cel

infusion and throughout the course of the study must be reported directly to the MAH (Sections 11 and 12).

		Post-HSCT Follow-up			
	Baseline /				Years 2 to 15
Registry Variable	Day 0	Day 100	Month 6	Year 1	(annual)
Informed consent / assent	Х				
Primary disease diagnosis					
β-thalassemia or SCD diagnosis	X				
Genotype	X				
Exposure					
Transplant date / Day 0 designation	Х				
Exa-cel or allo-HSCT	X				
Safety outcomes					
Neutrophil recovery		Х	Х		
Platelet recovery		Х	Х	X	
New malignancy		Х	Х	X	X
New or worsening hematologic disorder		Х	Х	X	Х
Mortality, cause		Х	X	Х	Х
Effectiveness outcomes					
Primary disease severity events (RBC transfusion, VOC) ^a	X	X	Х	X	Х
Hb measures (total Hb, HbF) a, b	Х	Х	X	X	X
Iron concentration measures ^{a, b}	Х	Х	X	X	X
Disease-related end organ damage / dysfunction diagnoses ^a	X	X	Х	X	Х
Iron overload management ^a	Х	Х	Х	X	X
Additional key variables					
Age at initial disease diagnosis	Х				
Age (at transplant)	Х				
Sex	Х				
Race, ethnicity (US only)	Х				
Country of transplant	Х				
Payor type (US only)	Х				
Performance score	Х	Х			
Comorbidity index	X				
Infused CD34 ⁺ Dose ^c	Х				
Donor type ^d	Х				
Cell source ^d	Х				
Mobilization and conditioning regimen	Х				
Height ^b	Х	Х	Х	Х	Х
Weight ^b	Х	Х	Х	Х	Х
Disease-related therapies ^a	X	X	Х	X	Х
Additional laboratory measures ^{a, b}	X	X	Х	X	Х
Transplant-related complications		X	Х	X	

Table 2Data Collection Schedule

Table 2Data Collection Schedule

		Post-HSCT Follow-up			
Degister Verichle	Baseline /	Dog 100	Month 6	Voor 1	Years 2 to 15
Registry variable	Day 0	Day 100	Month o	rear 1	(annuar)
Pregnancy, outcome		Х	X	Х	X

allo-HSCT: allogeneic HSCT; exa-cel: exagamglogene autotemcel; Hb: hemoglobin; HbF: fetal Hb; HSCT: hematopoietic stem cell transplantation; RBC: red blood cell; SCD: sickle cell disease; US: United States; VOC: vaso-occlusive crisis Note: Time to event will be captured for all variables, where specified in Section 9.3.

^a Data on history pre-HSCT will be collected retrospectively at enrollment. This may include: transfusion (TDT and SCD) and/or severe VOC (SCD only) rates in the 1 year prior to preparative regimen initiation, historic diagnoses, pre-transplant therapies in the 1 year prior to HSCT, recent pre-transplant laboratory findings, etc.

^b The non-missing measurement most proximal to the data report date.

^c Exa-cel Cohorts only

^d Allo-HSCT Cohorts only

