9.7.1 Definition of Study Periods

For safety and effectiveness outcome analyses within the Exa-cel and Allo-HSCT Cohorts the pre-transplant and post-transplant periods will be defined as described below and illustrated in Figure 2:

- **Day 0 (transplant date)** is defined as the day of exa-cel product or allogeneic donor cell infusion, depending on cohort, as reported to the registries.
- **The pre-transplant / baseline period** will be broadly defined as the period prior to Day 0, with the length of the period varying depending on the study measures being evaluated:
 - For the *primary disease severity* measures (see Section 9.3.4 Effectiveness Outcome Variables) and *disease-related therapies* (see Section 9.3.5), the baseline period will be defined as 1 year prior to initiation of the conditioning regimen.
 - For *laboratory measures*, baseline will be defined as the non-missing measure most proximal, but prior to treatment initiation. This includes effectiveness measures such as total Hb, Hb fractionation (e.g., % HbS for SCD) and serum ferritin (see Section 9.3.4) as well other laboratory measures (see Section 9.3.5).
 - For pre-transplant *disease-related end-organ damage or dysfunction* (see Section 9.3.5) baseline will be defined as any time prior to the transplant.
 - Other variables such as patient demographics, pre-transplant height, weight and health status will be as reported at the most recent time point prior to transplant.
- The post-transplant period will continue for up to 15 years after the final enrolled patient's Day 0. For each patient, Year 1 will include events, new diagnoses or findings, and/or therapies initiated (or continued) within the first 365 days after Day 0; Year 2 will include the same occurring from patient day 366 to day 730, etc. Year 1 will further include the following time intervals based on existing transplant registry reporting: Day 0 to Day 100, Day 100 to 6 months, and 6-month to 1-year reporting. All patients, both exa-cel treated or comparator, will be followed for up to 15 years. Patients will be censored to last reported timepoint only after 2 years of loss to follow-up.

Figure 2 Study Periods

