9.9 Limitations of the Research Methods

9.9.1 Limitations of Registry Data Collection

The transplant registries used for this study have definite strengths for the collection of real-world data, particularly for those outcomes that are transplant-specific such as neutrophil recovery and secondary malignancy development. While registry data to be collected for this study is very broad, it may not be as granular as clinical trial data. This is an expected limitation of observational, real-world studies. Where feasible, additional data collection is being integrated in consultation with the registry personnel, balancing appropriate level of detail in the data collection to meet the study objectives with the burden of time placed on transplant personnel and their ultimate willingness to participate in the study.

For example, it is deemed by the registries that collection of the laboratory results most proximal to the patient's data reporting period (e.g., 6 months, 1 year) is sufficient to identify any long-term abnormalities and allows to limit the burden of data entry placed on the transplant center personnel. While longitudinal laboratory results will only be collected at pre-specified timepoints, it is unlikely that safety events will be missed due to this limitation because a broad range of hard endpoints (i.e., disease diagnoses) are included in this study and uploaded into the registry by transplant center personnel.

In a similar manner, registries will collect comprehensive data on number of severe VOC events among patients with SCD in each reporting interval and time from HSCT to most recent severe VOC event but will not capture the date of each possible severe VOC event over the 15-year study duration. This approach was deemed to be optimal, allowing the capture of information necessary to meet the study objectives without limiting the feasibility of the study by the undue burden of data collection on the participating transplant centers.

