9.9.4 Missing Data

Due to the observational nature of this study, some patients may have missing visits and/or missing data. Data may be missing from either the pre-treatment or post-treatment periods. The registries included in this study incorporate robust systems to minimize missing data. As described in Section 9.8, participating centers will be incentivized and monitoring procedures and source data verification will be put in place to maximize the data quality and completeness. All efforts will be made to ensure that the level of missing data for key variables of interest does not exceed 20% (considered acceptable to support regulatory decision-making based on the published literature).³⁴

The study progress reports will include statistics on the percent missing data for the key variables of interest.

Although no imputation of missing data will be conducted in the course of statistical analyses, if data are missing for more than 20% of the patients, additional analyses may be performed to understand if there are any systematic differences between patients with and without missing data to assess the direction and magnitude of potential bias.

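### Table 2 footnote b does not limit Hb, iron, height, weight and laboratory values to the current reporting interval, and the laboratory baseline anchor is undefined

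*Protocol*

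**What the plan says.** **Follow-up values.** Table 2 attaches footnote b to Hb measures, iron concentration measures, height, weight and additional laboratory measures, at baseline and at every later report to Year 15. The footnote reads: "The non-missing measurement most proximal to the data report date". Section 9.9.1 describes the same idea as "collection of the laboratory results most proximal to the" patient's reporting period, and adds that "longitudinal laboratory results will only be collected at pre-specified timepoints". Neither place states a window or an earliest admissible date.

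**Baseline.** Section 9.7.1 has its own laboratory rule: "baseline will be defined as the non-missing measure most proximal, but prior to treatment initiation". The baseline period in general "will be broadly defined as the period prior to Day 0". For disease severity and disease-related therapies, "the baseline period will be defined as 1 year prior to initiation of the conditioning regimen".

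**Analysis.** Section 9.7.4 summarizes Hb and iron at each timepoint only in patients who have an observation there, and makes change from baseline optional. Section 9.9.4 states that "no imputation of missing data will be conducted in the course of statistical analyses". It foresees a comparison of patients with and without data when more than 20% are missing.

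**The concern.** A rule that takes the nearest non-missing value returns something whenever any value exists. If a patient has no new liver or cardiac MRI at an annual report, the nearest one may be a year or more old. At Day 100 it may pre-date the transplant. The entry would then count as an observation at that timepoint.

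Section 9.3.4 uses Hb fractions and iron burden to follow graft function and durability. Old values entered as current would slow the apparent fall in iron and could blur a later change in either direction. They would also make completeness look better than it is, so the 20% check might not operate for the measures most likely to be missing.

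At baseline, a sample taken during conditioning could reflect the conditioning regimen and not the patient's prior state. That would distort any baseline summary or change from baseline that used it.

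**Working it through.** The protocol gives no figure to reproduce. The check sets the sections side by side, then illustrates the literal rule.

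**1. Are comparable variables bounded?** Yes. Chelation and phlebotomy are recorded since the last visit (Section 9.3.4), and disease-related therapies since the prior visit (Section 9.3.5). Patient-years are bounded by days in Section 9.7.1 ("Year 2 will include the same occurring from patient day 366 to day 730"), for events, new diagnoses or findings, and therapies. Laboratory values are not named there. If findings is meant to include them, footnote b is looser than Section 9.7.1; if not, they have no bound at all.

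**2. How old can a selected value be?**
- Day 100 report: a value from Day −10 lies 100 − (−10) = 110 days away. It is the nearest unless another value falls after Day −10 and before Day 100 + 110 = Day 210. If values after the report date do not count, the search ends at Day 100.
- Annual report: a value about 365 days old is selected when nothing nearer exists, and the footnote does not stop at 365 days.

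**3. Which event anchors the laboratory baseline?** Section 9.7.1 uses two anchors: Day 0 for the general period and the start of conditioning for severity and therapies. Treatment initiation is tied to neither.
- If it means infusion, a Day −1 sample qualifies.
- If it means the start of conditioning, a sample taken during conditioning is excluded.

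Footnote b also covers the Baseline / Day 0 column, and Section 9.2 has baseline data entered at or near transplant. The value nearest that report could therefore fall during conditioning. The anchors diverge elsewhere too: baseline therapies cover the year before conditioning in Section 9.7.1, but the year before HSCT in Section 9.3.5 and in footnote a to Table 2.

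**4. Illustration, with every input assumed.** Liver iron is 10 mg/g at baseline in all patients and falls 30% a year. MRI is done each year in a random fraction q of patients, close to the report. The most recent value is entered if there is no new one.

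True values at baseline and Years 1 to 3: 10; 7.0; 4.9; 3.43.

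Reported Year 3 mean = q(3.43) + q(1−q)(4.9) + q(1−q)²(7.0) + (1−q)³(10)

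- q = 0.5: 1.715 + 1.225 + 0.875 + 1.250 = 5.07; 5.07/3.43 = 1.48, or 48% too high. Apparent missingness is 0%, true missingness 50%.
- q = 0.8: 2.744 + 0.784 + 0.224 + 0.080 = 3.83; 3.83/3.43 = 1.12, or about 12% too high. Apparent missingness is 0%, true missingness 20%.

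Because scanning is random here, the mean in patients actually scanned at Year 3 would be the true 3.43. The whole discrepancy comes from admitting older values. In the q = 0.8 case the check would not operate even with correct reporting, since 20% is not more than 20%.

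**The case against.** The strongest reply is that carry-forward is nowhere stated. Restricting summaries to patients with an observation presupposes that a timepoint can be empty. Section 9.9.1 ties laboratory values to the reporting period and to set timepoints, Section 9.9.4 rules out imputation, and Table 2 places Day 100 under post-HSCT follow-up. All of this suggests that interval-bound values are intended. Visit windows are also commonly left to the statistical analysis plan, and the registry forms and completion guidelines, which are not shown, may already ask for a date.

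Much of this stands. A reader might infer that the plan carries old values forward; the documents support only that the footnote permits it. A reader might likewise infer that baselines will be post-conditioning; that follows only if treatment initiation means infusion. Nor would every change from baseline be affected: Section 9.7.4 makes that analysis optional and only for effectiveness measures, and Section 9.7.5 plans plain summaries for the additional laboratory measures.

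What does not answer the point is deferral to the analysis plan. Footnote b sits in the collection schedule and so governs what centers enter. If one value is entered without its date, no later window can separate a new MRI from an old one. The protocol text does not require that date. Centers also have reason to fill fields: Section 9.8.1 ties the full EBMT documentation fee to at least 80% completeness, and Section 9.8.2 requires 100% of supplemental study data for CIBMTR good standing.

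**Conclusion.** The point holds as a defect of wording in a collection rule. Footnote b does not confine values to the current reporting interval, which fits poorly with the observed-only summaries of Section 9.7.4 and the no-imputation rule of Section 9.9.4. The laboratory baseline uses an undefined anchor in a section that employs two different ones.

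The likely direction is damped change and understated missingness, mainly for infrequent measures such as MRI. The size cannot be derived from the documents. The 48% and 12% figures rest wholly on the assumed scan frequency and rate of decline, concern liver iron only, and say nothing about Hb or HbF. The measures affected serve the secondary effectiveness objectives and supporting laboratory summaries; the primary safety outcomes in Section 9.3.3 are not governed by footnote b. The correction is worth making before the study-specific forms are finalized, which Section 9.3 places at protocol approval.

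**What to change.** **Footnote b.** Replace with: *the measurement closest to the report's target date among those taken after the previous report's assessment date (after Day 0 for the Day 100 report) and up to the current assessment date; record the measurement date; if none, record as missing.*

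Bounding by assessment dates is safer than fixed windows of days 365(k−1)+1 to 365k. For Year 1 such a window (days 1 to 365) would overlap the Day 100 and 6-month intervals. A Year 3 visit on day 1100 would lose its own same-day results, because the window ends at day 3 × 365 = 1095.

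**Section 9.7.1.** Define the laboratory baseline as the last value before the start of the conditioning regimen, the anchor already used there for disease severity, in all cohorts. Make the Baseline column under footnote b agree with it.

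**Cost.** One footnote, one bullet, and a measurement date wherever the forms do not already collect one. Reported missingness for MRI and other infrequent measures will rise to its true level.
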